8.2. Secondary Efficacy Endpoints

8.2.1. Mycological outcomes

The percentage of subjects with mycological eradication (negative culture for growth of *Candida* species) at the TOC visit will be analyzed by *Candida* Species of the baseline yeast and overall, using the same inferential analysis employing the same methods as for the primary analysis as noted in Section 8.1.1. The subjects with missing TOC visit data for the mycological outcome will be imputed as mycological persistence using the NRI method described in Section 4.4.

Mycological outcomes will be assessed at the specified visit according to the following definitions.

- Mycological Eradication: A subject with negative culture for *Candida* species without need for further antifungal treatment prior to the TOC visit;
- Mycological Persistence: A subject with a positive culture for *Candida* species or use of additional vulvovaginal or systemic antifungal therapy prior to the TOC visit. For the subject who early terminated before TOC visit and received additional vulvovaginal or systemic antifungal therapy prior to the early termination visit, the subject is considered a mycological persistence.

In addition, a sensitivity analysis will be conducted based on the mITT set where subjects with the imputed mycological outcome using the NRI method at the TOC visit will be removed from the analysis.

The same analysis will be done for the percentage of subjects with mycological eradication (negative culture for growth of *Candida* species) at the FU visit.

The change of mycological outcomes will be summarized in shift tables comparing the testing results at TOC visit with those at FU visit.

The analyses for mycological outcome will only be conducted for the mITT and PP sets.

In addition, a summary table will be presented to include CLSI MIC range, mode, MIC50, and MIC90, based on the ITT and mITT sets by treatment group for the following MIC results:

- MIC results for SCY-078 and fluconazole (FLU) at 24 hours against candida species isolates obtained at TOC visit;
- MIC results for SCY-078 at 48 hours against candida species isolates obtained at TOC visit.

Frequency cross-tabulations of mycological persistence at baseline versus mycological eradication at TOC visit will be presented by treatment group by candida species isolates obtained at baseline.

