18.0 Analytical Plan

All statistical processing will be performed using SAS[®] version 9.3 or later, unless otherwise stated. All statistical tests will be two-sided and interpreted at a 5% significance level.

Descriptive statistics (i.e., mean, standard deviation, median, minimum, maximum, etc.) will be provided for all continuous variables; frequencies and percentages will be presented for incidence and categorical variables. For parameters measured over time, observed values and changes from Baseline will be described for each time point.

The clinical cure and mycological eradication rates will be described by baseline *Candida* species, when the number of isolates per species allows.

All analyses will be presented by treatment group. Unless otherwise stated, data will be analyzed as is with no imputation. No adjustment for multiplicity will be employed.

A Statistical Analysis Plan (SAP) describing all statistical analyses in detail will be provided as a separate document. The SAP will be finalized prior to unblinding of the study treatments.

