8.1.1. Primary Analysis

The primary efficacy analysis will be performed on the mITT set at the TOC visit and will compare the proportion of subjects, in the treatment and placebo groups, who have a clinical cure at the TOC visit.

The number and percentage of subjects with clinical cure at the TOC visit will be presented by treatment group. A Cochran Mantel Haenszel (CMH) test adjusted for site and diabetes mellitus diagnosis (Yes or No) will be performed to assess the statistical significance of a difference between treatment groups in the primary efficacy analysis. Mathematically stated:

$$\begin{aligned} H_0: \text{TOC Clinical Cure Rate Oral ibrexafungerp 300-mg dose} &= \text{TOC Clinical Cure Rate Placebo} \\ H_1: \text{TOC Clinical Cure Rate Oral ibrexafungerp 300-mg dose} &\neq \text{TOC Clinical Cure Rate Placebo} \end{aligned}$$

The p-value, odds ratio and 95% confidence interval will be presented in the ibrexafungerp 300-mg treatment arm compared to the placebo arm. Missing data for clinical outcome will be imputed using the NRI method described in Section 4.4. Additional summarizations will be performed by Candida Species of the baseline yeast, and the same inferential analysis will be performed, as appropriate.

The same inferential analysis employing the same methods as for the primary analysis will be performed for the ITT set and PP set to assess clinical cure at TOC visit. Missing data for clinical outcome will be imputed using the NRI method described in Section 4.4. No adjustment of type I error will be performed as these analyses are considered supportive to the primary analysis.

A sensitivity analysis using the mITT set will be performed where subjects with the imputed clinical outcome using the NRI method at TOC visit will be removed from the analysis.

Two subgroup analyses will be performed depending on Body Mass Index category ($\leq 35 \text{ kg/m}^2$ or $> 35 \text{ kg/m}^2$).

Analysis of time to resolution of signs and symptoms after initiation of study drug will use Kaplan-Meier method to estimate the median resolution time and its 2-sided 95% confidence intervals (CIs) based on the ITT, mITT, and PP sets. The time to resolution of signs and symptoms after initiation of study drug is defined as time (days) from first dose of study medication to the first resolution of signs and symptoms. Subjects who discontinued early will be censored at the last available assessment.

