8.2.2. Overall Outcome

The percentage of subjects with clinical cure and mycological eradication (overall outcome) at the TOC visit will be analyzed by Candida Species of the baseline yeast and overall, using the same inferential analysis employing the same methods as for the primary analysis as noted in Section 8.1.1. The subjects who cannot determine the overall outcome at the TOC visit will be removed from the analysis and no missing data will be imputed for both clinical outcome and mycological outcome.

Overall outcomes will be assessed at the TOC Visit (Day 11) according to the following definitions:

- Overall Success: A subject with the achievement of both a clinical cure and mycological eradication;
- Overall Failure: A subject with either clinical failure or mycological persistence.

The analyses for overall outcome will only be conducted for the mITT and PP sets. The overall outcomes will be listed with baseline species referenced aside in a listing.

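### The SAP extends the primary site-by-diabetes CMH inference to each baseline Candida species with no minimum count, where the protocol planned only description; in uncommon species the output often breaks down

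*SAP*

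**What the plan says.** Protocol 18.0 (repeated in the synopsis) is descriptive: "The clinical cure and mycological eradication rates will be described by baseline" species, and only "when the number of isolates per species allows". It names two outcomes, clinical cure and eradication. Protocol 18.6.2 plans the CMH test for each endpoint as a whole, adjusted for site.

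The SAP goes further:

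- **Eradication (8.2.1):** analysed by Candida "Species of the baseline yeast and overall, using the same inferential analysis employing the same methods as for the primary analysis".
- **Overall outcome (8.2.2):** "will be analyzed by Candida Species of the baseline yeast and overall, using the same inferential analysis employing the same methods". Section 8.2.3 uses the same wording for symptom resolution at follow-up.
- **Clinical cure (8.1.1):** "Additional summarizations will be performed by Candida Species of the baseline yeast, and the same inferential analysis will be performed, as appropriate".

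The method carried over is the one in 8.1.1, a CMH "test adjusted for site and diabetes mellitus diagnosis (Yes or No) will be performed". Its output is also fixed there: "The p-value, odds ratio and 95% confidence interval will be presented".

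No section gives a minimum species count or a rule for pooling small sites. SAP section 11 lists two changes from the protocol, ANCOVA in place of ANOVA and the added diabetes factor. By-species testing is not among them.

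**The concern.** A CMH test and a Mantel-Haenszel odds ratio draw information only from strata that contain both arms. About 30 sites (Protocol 10.4) crossed with diabetes give up to 60 strata. Randomisation is stratified by diabetes only (Protocol 10.2, SAP 4.2), so nothing balances the arms within a site. Within an uncommon species, many women will be alone in their stratum or there with women of one arm only, and so drop out of the comparison.

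The background sections of both documents give reduced fluconazole susceptibility of *C. glabrata* as one reason for a new agent, so readers will look at the non-albicans rows. A large p-value beside a degenerate odds ratio could be taken as absence of effect in that species, when the method could barely have shown one.

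**Working it through.** **1. The plan's own figure.** The only power statement concerns the whole trial: 282 evaluable women for 90% power, 50% v 30%, 2:1, two-sided 5%. The pooled rate is (2 × 0.5 + 0.3)/3 = 0.4333.

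Placebo n = [1.96·√(0.4333 × 0.5667 × 1.5) + 1.2816·√(0.25/2 + 0.21)]² / 0.2² = (1.190 + 0.742)²/0.04 ≈ 93.2, so 94. Total 94 + 188 = 282, which agrees. The documents give no by-species figure.

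**2. Inputs.** From the documents: about 30 sites, 2:1 allocation, 50% v 30%, and 20% without a positive baseline culture, so an mITT set of about 366 × 0.8 = 293. Assumed, because the documents are silent: 25 or 40 women in a species (about 9% and 14% of 293), 10% with diabetes, and the spread of site sizes. The adjustment is read as cross-classified site-by-diabetes strata, and the odds ratio as Mantel-Haenszel.

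**3. Women in two-arm strata, 30 equal sites.** For n = 25, a given non-diabetic stratum has probability 0.9/30 = 0.03. An ibrexafungerp woman has no placebo woman in her stratum with probability (1 − 0.03/3)²⁴ = 0.786. A placebo woman has no ibrexafungerp woman with probability (1 − 0.02)²⁴ = 0.616. The two-arm share is 2/3 × 0.214 + 1/3 × 0.384 = 0.271. The same steps for diabetic strata (0.1/30) give 0.035. Overall: 0.9 × 0.271 + 0.1 × 0.035 = **25%**. For n = 40 the result is 0.9 × 0.398 + 0.1 × 0.056 = **36%**.

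**4. Simulation.** Women are placed at random in site-by-diabetes strata and allocated 2:1. The odds ratio counts as unusable (zero, infinite or undefined) when Σ(ad/T) = 0 or Σ(bc/T) = 0 over strata, where a, b are responders and non-responders on ibrexafungerp, c, d on placebo, and T is the stratum total.

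| Site sizes | n | Women in two-arm strata | Odds ratio unusable | CMH power |
|---|---|---|---|---|
| 30 equal | 25 | 25% | 76% | 2% |
| 30 uneven (Dirichlet 1) | 25 | 38% | 56% | 5% |
| 30 very uneven (Dirichlet 0.5) | 25 | 46% | 45% | 7% |
| 30 equal | 40 | 36% | 35% | 10% |
| 30 uneven (Dirichlet 1) | 40 | 50% | 18% | 12% |
| 30 very uneven (Dirichlet 0.5) | 40 | 59% | 12% | 13% |

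Repeat runs differ by a few points. At n = 25 the very uneven layout gave 41–45% unusable; at n = 40 the equal layout gave 34–37%. Over layouts and runs the ranges are 41–76% and 12–37%.

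**5. Sensitivity (equal sites).** At n = 25, moving diabetes from 0% to 20% moves unusable odds ratios from 69% to 79%, so site drives most of the loss. With 63% v 30% (63% being the Phase 2b eradication rate quoted in Protocol 7.1) and 8% diabetes, the figures are 75% at n = 25 and 41% at n = 40. At n = 250, or in the full mITT set of about 293, the odds ratio was always estimable.

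**6. Unstratified comparison.** With 17 v 8 women, the table has an empty cell essentially only if all or none of the placebo women respond: 0.7⁸ + 0.3⁸ = 5.8%. With 27 v 13 it is 0.7¹³ ≈ 1.0%. When arm sizes also vary at random, these become about 7% and 1–2%.

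Power at 17 v 8: pooled rate 0.436, null SE √(0.436 × 0.564 × (1/17 + 1/8)) = 0.2126, alternative SE √(0.25/17 + 0.21/8) = 0.2024. Then Φ[(0.20 − 1.96 × 0.2126)/0.2024] = Φ(−1.07) = **14%**. At 27 v 13 the same formula gives Φ(−0.80) = **21%**.

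**The case against.** Several objections limit the point, and most of them stand.

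- **Assumed counts and layout.** A reader might infer that stratification discards most women in any small species and usually leaves no odds ratio. The documents give no species counts or site sizes. Equal sites are the harshest of the layouts tried. At 40 women with uneven sites, half or more stay in two-arm strata and only about one odds ratio in six to eight is unusable.
- **Source of low power.** A reader might blame stratification for the lack of power. It makes matters worse, but an unstratified test reaches only 14–21%. Small numbers are the main cause, and a wide unstratified interval can also be misread as no effect.
- **Extent of the conversion.** A reader might infer that the SAP turned every by-species table into a test. Only eradication is converted without qualification. Cure keeps discretion ("the same inferential analysis will be performed, as appropriate"). Overall outcome and follow-up symptoms had no by-species display in the protocol, so those tests are additions.
- **Discretion by cross-reference.** Sections 8.2.1 to 8.2.3 point back to 8.1.1, so its discretion might be carried across. That reading is possible, but those sections do not say it, and no threshold is given on either reading.
- **Existing descriptive output.** Section 8.2.1 already plans cross-tabulations by treatment and baseline species, so counts would be visible beside a degenerate odds ratio. That softens the risk but does not justify the test.
- **Estimator.** The SAP says only odds ratio. The unusable rates depend on reading it as Mantel-Haenszel.

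**Conclusion.** The point holds for uncommon species. On the text alone, the SAP moves from description to inference for eradication, adds by-species tests for two further outcomes, sets no minimum count, and does not declare this in section 11. None of that rests on an assumption.

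The size does rest on assumptions. For a species of 25 to 40 women at about 30 sites, the prescribed odds ratio is unusable in anything from 12% to 76% of trials, against 1–7% unstratified. The share of women in two-arm strata is 25–46% at n = 25 and 36–59% at n = 40. The result is driven by species count and site sizes, neither of which the documents give. A species that makes up most of the mITT set is not affected.

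A reader might infer that the trial's conclusions are at risk. The documents do not support that: no objective or endpoint is species-specific, and the overall analyses of the primary and listed secondary endpoints are untouched. This is a minor correction to exploratory output.

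**What to change.** In SAP 8.1.1 and 8.2.1 to 8.2.3, make by-species results descriptive: n/N and percentage per arm, with an unstratified exact or Newcombe 95% confidence interval for the difference and no p-value. If a comparison is kept for the commonest species, make it unstratified or stratified by diabetes only, and list it in section 11 as a change from the protocol.

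The cost is SAP wording and somewhat simpler programming. The downside is that uncommon species get no p-value, and at these numbers one would carry almost no information.

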14.10 Vulvovaginal Samples for KOH and Fungal Culture

At Screening, a vulvovaginal specimen will be obtained for direct microscopic examination with 10% KOH. Subjects must have a positive KOH test at Screening to be randomized to one of the study treatment groups. The Screening KOH will be assessed at the site by the investigator or qualified designee. A vaginal sample will also be obtained at Screening and at the TOC visit for fungal culture and species identification by the central laboratory and for susceptibility testing against ibrexafungerp and additional antifungal agents (per CLSI M27-A3 guidelines). If there is persistence or recurrence of vulvovaginal symptoms, additional vulvovaginal specimens will be collected for KOH testing at the TOC and at the FU visits, and for fungal culture at the FU visit. Samples will also be obtained at any unscheduled visit, if needed.

If the subject experiences persistence or worsening or recurrence of symptoms that per the investigator's assessment (e.g. symptoms ≥ 3) warrant the use of rescue antifungal therapy, a vaginal examination with collection of samples for KOH (assess at the site) and culture should be completed prior to initiation of rescue therapy. If the KOH test is negative, the investigator should consider other causes for the persistence or worsening of the symptoms and antifungal rescue medication may not be indicated. If the collection of the vaginal culture is not possible prior to the initiation of the rescue therapy, it should still be collected as soon as possible after rescue therapy is given.

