8.2.3. Symptom Outcome

The percentage of subjects with complete resolution of symptoms at the Follow-up (FU) visit will be analyzed by Candida Species of the baseline yeast and overall, using the same inferential analysis employing the same methods as for the primary analysis as noted in Section 8.1.1. The subjects with missing Follow-Up data for the symptom outcome will be imputed as symptom persistence using the NRI method described in Section 4.4.

Symptom outcomes will be assessed at the FU Visit according to the following definitions:

- Symptom Resolution: All symptoms are absent (score = 0) without need for further antifungal treatment or topical vaginal drug therapy for the treatment of vulvovaginal irritation/pruritus prior to or at FU visit;
- Symptom Persistence: No response to therapy or incomplete resolution of symptoms or use of additional vulvovaginal or systemic antifungal therapy or topical vaginal drug

therapy for the treatment of vulvovaginal irritation/pruritus prior to or at FU visit. For the subject who early terminated before the FU visit and received additional vulvovaginal or systemic antifungal therapy or topical vaginal drug therapy for the treatment of vulvovaginal irritation/pruritus prior to or at the early termination visit, the subject is considered a symptom persistence.

In addition, a sensitivity analysis will be conducted based on the mITT set where the subjects with the imputed symptom outcome using the NRI method at the FU visit will be removed from the analysis.

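### The follow-up mycological analysis counts antifungal use only up to TOC, so a woman first treated between TOC and FU whose later FU culture is negative is scored as eradicated

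*SAP*

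**What the plan says.** SAP 8.2.1 gives one pair of mycological definitions and introduces them with "Mycological outcomes will be assessed at the specified visit according to the following definitions". Three pieces of text fix the antifungal window:

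- Eradication is "A subject with negative culture for *Candida* species without need for further antifungal treatment prior to the TOC visit".
- Persistence is a positive culture or "use of additional vulvovaginal or systemic antifungal therapy prior to the TOC visit".
- The early-termination sentence begins "For the subject who early terminated before TOC visit and received additional vulvovaginal or systemic antifungal therapy prior to the early termination visit", so it reaches only women who left before TOC.

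The section then extends the work to the later visit: "The same analysis will be done for the percentage of subjects with mycological eradication" at FU. It also plans shift tables from TOC to FU. No separate FU definition is given.

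For symptoms at that same visit, SAP 8.2.3 counts antifungal or topical vaginal therapy "prior to or at FU visit" as symptom persistence.

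**The concern.** The definitions are written to serve any visit, but the cut-off inside them names TOC. SAP 8.2.3 moves the cut-off to FU and SAP 8.2.1 does not. A negative FU culture obtained after an antifungal taken between the two visits may reflect that antifungal and not the randomised treatment, yet the rule credits it to the randomised arm.

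What is at stake is the FU eradication comparison, for which p-values, odds ratios and confidence intervals are planned by the primary-analysis method. If women on placebo take antifungals after TOC more often, the comparison is pulled towards no difference. Where the intended window must be guessed, two programmers can also reach different results from the same data.

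**Working it through.** **The plan's own figure.** The documents give no expected rate or power for FU eradication. The only powered figure is 282 evaluable subjects for the primary endpoint (SAP 4.1: 30% vs 50%, 2:1, two-sided 5%, 90% power). With pooled rate (0.30 + 2 × 0.50)/3 = 0.4333, placebo n = [1.960 × √(1.5 × 0.4333 × 0.5667) + 1.2816 × √(0.30 × 0.70 + 0.50 × 0.50/2)]² / 0.20² = 93.2. That rounds up to 94, and 94 + 188 = 282. The figure reproduces, and this point does not alter it.

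**Applying the definitions literally at FU.**

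| Woman | Mycology (SAP 8.2.1) | Symptoms (SAP 8.2.3) |
|---|---|---|
| Antifungal before TOC, FU culture negative | Persistence | Persistence |
| First antifungal after TOC, then FU culture negative | **Eradication** | Persistence |
| First antifungal after TOC, FU culture positive | Persistence | Persistence |
| First antifungal after TOC, no FU culture | Persistence (missing, SAP 4.4) | Persistence |

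Only the second row goes wrong.

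**Looking for an overriding rule.** SAP 4.4 turns missing FU values into failures and has no rule for rescue. The mycological definitions in Protocol 18.6.1 rest on culture alone. Neither changes the second row.

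**Whether the second row can occur.** Protocol 11.4 has FU procedures completed when rescue is given after TOC. Protocol 14.10 wants the culture before rescue, but when that is not possible says "it should still be collected as soon as possible after rescue therapy is given". Protocol 13.1 provides for recording antifungals taken after TOC. So the case can arise, though the documents do not say how often.

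**Size.** Let r be the proportion in an arm whose first antifungal comes after TOC, and q the share of those women with a negative culture taken afterwards. Each arm's FU eradication rate rises by r × q. If q is the same in both arms:

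loss in the treatment difference = (r placebo − r active) × q

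The documents supply neither r nor q. As assumptions only:

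- Placebo excess 10 to 15 points.
- q from 12% (20% cultured after treatment × 60% of those negative) to 40% (50% × 80%).
- Low end: 10 × 0.12 = 1.2 points.
- High end: 15 × 0.40 = 6.0 points.

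With about 98 placebo women in the mITT set (366 × 0.8 / 3 = 97.6), this is roughly 1 to 6 extra women scored as eradicated on placebo, beyond the proportion so scored on active.

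**The case against.** **Intent.** Because the definitions are tied to whichever visit is being assessed, the authors may have meant the window to move with it. That is plausible, but the text names TOC three times, and SAP 8.2.3 shows how the authors write an FU window when they want one. The wording still needs settling.

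**Rarity.** Culture is meant to precede rescue, later sampling is a fallback, and no further visit follows post-TOC rescue. This stands. It limits the case mainly to sampling that followed rescue and to women who treated themselves after TOC.

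**Standing of the analysis.** SAP 3.2.2 and Protocol 9.2 list mycological eradication at TOC only. This also stands.

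A reader might infer more than the documents support:

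- *A bias of 3 to 10 points, from Phase 2b rescue.* Protocol 7.1 reports 7 rescued women on fluconazole and 1 on the 600-mg dose. Over the cure denominators of 24 and 27, that is about 29% vs 4%, and 25 points × 12% to 40% gives 3 to 10. But fluconazole is not placebo, rescue is not split into before and after TOC, and no rescue denominator is stated.
- *Misclassification at TOC.* Antifungal use before TOC is already persistence. Rescue given at the visit after sampling cannot affect that culture. What remains is marginal, and the overall outcome is protected because rescue at TOC is already clinical failure under SAP 8.1.
- *Rescued women as a large share of FU data.* The main analysis uses all women in the set as denominator, with missing cultures scored as persistence. No figure supports a large share.
- *Biased shift tables.* They are described as comparing testing results and may show raw cultures, which would not be an error.

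**Conclusion.** The point holds for the FU eradication analysis. SAP 8.2.1 as written scores as eradicated a woman whose negative FU culture follows an antifungal first taken between TOC and FU, and it disagrees with SAP 8.2.3 about the same woman at the same visit. The primary endpoint and sample size do not change, and the listed TOC endpoints are essentially unaffected.

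The direction is conditional: against ibrexafungerp if post-TOC antifungal use is commoner on placebo. That is plausible given the assumed cure rates of 50% and 30%, but it is not shown. The size of about 1 to 6 points rests wholly on the assumed excess and share, and on the share being equal in the two arms. It is a range for judging importance, not an estimate. The correction is worth making because a planned inferential result depends on it and little work is needed.

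**What to change.** Before unblinding, amend SAP 8.2.1 as follows:

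1. For the FU analysis, score as mycological persistence any woman with additional vulvovaginal or systemic antifungal use after the first dose of study drug and before the FU culture sample.
2. Extend the early-termination sentence to women who leave between TOC and FU.
3. Add a same-day rule, since Protocol 13.1 specifies medication dates and not times. When rescue and sample share a date, treat the culture as taken first, the order Protocol 14.10 asks for, unless the record shows otherwise.
4. Apply the same rule to the TOC-to-FU shift tables, or flag rescued women in them.

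Rescue given at the FU visit after sampling would still count under SAP 8.2.3 and not here. That difference is deliberate, because such a culture precedes the antifungal.

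The cost is a little programming and a few women moved to persistence. No visit, procedure or rescue instruction changes. A separate problem remains: FU cultures are scheduled only for symptomatic women, so under non-responder imputation an asymptomatic woman without one becomes persistence. This amendment does not address that.
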